14.2 Adverse Events (AEs)

14.2.1 General

Summaries of AEs will be presented using counts and percentages for the safety set.

Tables by preferred term and tables by system organ class (SOC) and preferred term will be sorted in descending order by the percentage of patients.

For all adverse event analyses, the date of first treatment will refer to the first date the patient ever received treatment with the Point of Care device. If a patient had stopped treatment then re-started, the date that they first started (including prior enrollments) will be used as the date of first treatment.

Unless otherwise specified, the summaries of adverse events will include the total number of patients experiencing the adverse event, the total number of events, and the adverse event rate (number of events per patient year). The total number of patient years will be calculated as follows for all adverse events (including pretreatment AEs):

$$\frac{\sum_{i=1}^n (\text{Date of Study Completion/Withdrawal} - \text{Informed Consent Date}) + 1}{365.25},$$

where n represents all patients in the Safety Set.

The total number of patient years will be calculated as follows for all treatment-emergent adverse events:

$$\frac{\sum_{i=1}^n (\text{Date of Study Completion or Withdrawal} - \text{Date of first treatment}) + 1}{365.25},$$

where n represents all patients in the Safety Set.

The adverse event rate will be calculated as:

$$\frac{\text{Total Number of Events}}{\text{Total patient years}}$$

For summaries of AEs presented by severity, the maximum severity will be presented if patients have multiple AEs within a SOC and preferred term (PT) with varying severity. If the severity of an adverse event is missing, then that adverse event will be classified as *severe*.

For summaries of AEs presented by relationship, the most conservative relationship will be presented if patients have multiple AEs within a SOC and PT with different relationships to either study product or typical PD therapy.

For patients who had re-enrolled, all adverse events will be listed and summarized.

Adverse event listings will be sorted by site ID, patient ID, and adverse event start date. They will include verbatim term, system organ class, preferred term, adverse event start date, adverse event end date, treatment start date, date of death (if relevant), causality, severity, action taken, seriousness, outcome, relationship to study device, relationship to typical PD therapy, relationship to another Baxter product, alternate causality, whether a treatment was provided, if it resulted in a change in concomitant medication, if it led to a SUSAR or UADE, and whether AE led to discontinuation from study. If an adverse event changes in severity, then each severity will be listed.

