## **3. INVESTIGATIONAL PLAN**

### **3.1 Overall Study Design and Plan**

This is an open-label, single arm, prospective, descriptive study. Up to 50 PD patients, who are stable on in-home APD using the AMIA or HomeChoice APD Cycler, will be enrolled in this study such that a total target of 30 evaluable patients complete the 12-week Study Treatment Period and the Follow-up Period.

During the Screening Period, all consenting patients will have a home assessment, including feed (tap) water analysis, to confirm their home environment is suitable for this study. Eligible patients will be followed for data collection regarding dialysate solution composition and safety while using the AMIA APD Solution Generation System.

---

[figure not shown]

Data will be collected throughout the duration of the study (approximately 18 weeks), including the Screening Period, Baseline Period (In-center Training Period), Study Treatment Period, Follow-up Period and the End-of-Study Visit/ Early Termination Visit. All AEs (not reported as medical history), product complaints (PCs) and device deficiencies (DDs) observed by the study personnel or reported by the patient during the course of the study will be documented from the time of signing the informed consent form (ICF) through the End-of-Study/ Early Termination Visit. The Principal Investigator (PI) or designee (e.g., sub-investigator) will assess each patient at the Screening Visit and on a weekly basis, according to standard of care. At a minimum, this assessment will include evaluation of BP, pulse rate, weight, fluid status and dialysis prescription.

Laboratory data will be collected at Screening and during the use of the AMIA APD Solution Generation System.

Evaluations will be taken as illustrated in [Appendix 1](#) and [Appendix 2](#). A trial scheme for the study is shown in [Figure 2](#) below.

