If a patient misses 4 consecutive days of prescribed therapy with AMIA APD Solution Generation System then the total Kt/Vurea assessment (between Weeks 5 - 8) should be deferred by 1 week to allow a full week of prescribed treatment using the AMIA APD Solution Generation System. Note: after patients have completed the total Kt/Vurea assessment required during Week 5, 6, 7 or 8 of the Study Treatment Period, in order to accommodate potential vacation/travel, patients may voluntarily interrupt investigational AMIA APD Solution Generation System treatment and perform standard of care PD therapy using the marketed AMIA or HomeChoice APD Cycler with currently available PD solution (e.g. Dianeal) up to 2 separate times with prior approval from the Investigator for up to 14 days in total; however, patients must complete a total of 12 weeks of cumulative therapy using the AMIA APD Solution Generation System.
16. Patients who withdraw from study due to missed therapy due to AMIA APD water device replacement may be allowed to rescreen to re-enroll up to 1 time, as assessed by Investigator and Sponsor.
17. Patient consistently misses more than 1 prescribed treatment per week, as assessed by the Investigator, over the course of the 12-week Study Treatment Period.
18. Other reason (with reason noted on the electronic case report form [eCRF]).

The reason for patient discontinuation or withdrawal from the study will be recorded on the appropriate page of the eCRF. A patient who signs the ICF but does not receive the

study treatment may be replaced. Patient who signs the ICF and receives the study treatment, and subsequently withdraws, or is withdrawn or discontinued from the study, will not be replaced.

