Patients who discontinue may be allowed to reenroll in the study. These patients will have separate but linked patient IDs (one for each enrollment in the study); this will be captured in the eCRF. These patients will be assigned one unique USUBJID during SDTM creation. Unless otherwise specified, for all patient-related analyses (e.g. demographics and baseline characteristics), these data will be summarized only once in tables, and all data will be listed next to their corresponding USUBJID in listings. For all device-related analyses (e.g. chemical composition testing of dialysis solution, microbiological testing of product water), all data gathered will be summarized and listed.

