11. TREATMENT COMPLIANCE AND EXPOSURE

11.1 Treatment Compliance

Compliance will be assessed regularly by the Investigator by reviewing the patient's Sharesource Platform data and eDiary entries. The patient will be instructed to complete the eDiary daily to document treatment activities including, but not limited to, the following:

- Treatment interruptions
 - Confirmation if the patient contacted dialysis center for support with a product or health-related issue
 - Confirmation if the patient was able to sleep during treatment
-
- 

- Treatment outcome (i.e., complete treatment, incomplete treatment) and reasons for incomplete treatment
- Confirmation if the patient altered their treatment parameters
- Investigational product supply requirements

The above eDiary data (with the exception of the investigational product supply requirements) will be summarized using frequencies and percentages for the number of patients experiencing at least one event and the total number of events per total treatments, and it will be summarized continuously using mean, standard deviation, minimum, median, and maximum for the total number of occurrences per patient. These data will also be listed.

For patients who have re-enrolled, the eDiary data will be pooled together.

Interruptions to therapy will be summarized using frequencies and percentages of the following:

- Number of interruptions per patient
- Reason for interruption
- Whether the patient was on standard of care PD therapy

The length of treatment interruption for all interruptions as well as per patient will be summarized for all interruptions using n, mean, median, standard deviation, minimum, and maximum.

The length of treatment interruptions for all interruptions will be calculated as follows:

$$\frac{\sum_{i=1}^t (\text{Treatment restart date} - \text{Date of interruption})}{t},$$

where i is each interruption and t is the total number of interruptions.

The length of total treatment interruptions per patient will be calculated as follows:

$$\frac{\sum_{i=1}^n \sum_{j=1}^m (\text{Treatment restart date} - \text{Date of interruption})}{n},$$

where j is each interruption per patient, m is the total number of interruptions per patient, i is each patient, and n is the total number of patients with an interruption.

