14.3.2 Device Alarms and Device Deficiencies/Product issues (DDs)

All device deficiency tables and listings will be done on the Safety Set. The number of device alarms and their relation to AEs will be summarized using frequency counts and percentages. The number of patients experiencing at least one device alarm and at least one device alarm due to an AE will also be summarized. Included in this summary will also be the number of patients experiencing at least one DD/product issue and at least one DD/product issue resulting in an AE, suspected unexpected serious adverse reaction (SUSAR), or unexpected adverse drug reaction (UADE). All of the above will also be summarized as a rate of events per total device installation days. This rate will be calculated by taking the number of events and dividing it by the total number of days the device is installed at a patient's home across all patients. The total number of device days will be calculated as follows:

$$\sum_{i=1}^n (\text{Date of last treatment} - \text{Date of home installation}) + 1,$$

where i is each patient and n is the total number of patients in the Safety Set.

All device deficiencies and product issues will be summarized by frequencies and percentages of both patients and total events, and by a rate of events per total number of device installation days for the following:

- Product causing DD
- Type of deficiency/product issue
- Occurrence of DD
- Whether the device gave an alert, alarm, or error message
- If there was a safety concern
- If the DD resulted in an AE or SUSAR/UADE

A listing will also be provided for all device deficiencies/product issues sorted by site ID, patient ID, and DD date. It will provide the product affected, date of onset, type, description, occurrence, whether a message was given (alert, alarm, error, or none), message description, if/what is a potential safety concern, and if/what AE resulted because of this DD.

For patients who had re-enrolled, all DDs will be listed and summarized.

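### The SAP 14.2.1 patient-year formulas do not give observed time for re-enrolled patients, so the adverse event rates are wrong whenever someone re-enrols

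*SAP*

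**What the plan says.** - **Numerator.** SAP 14.2.1: "For patients who had re-enrolled, all adverse events will be listed and summarized".
- **Denominator.** SAP 14.2.1 gives two patient-year formulas. For all AEs the span is completion or withdrawal date minus consent date. For treatment-emergent AEs it is completion or withdrawal date minus date of first treatment. Both are summed over i = 1 to n, "where n represents all patients in the Safety Set", with a + 1 printed after the closing bracket, and divided by 365.25.
- **Time origin.** For a patient who stopped and restarted, "the date that they first started (including prior enrollments) will be used as the date of first treatment".
- **Identity.** SAP 7.3 links the separate enrolment IDs: "These patients will be assigned one unique USUBJID during SDTM creation".
- **Observation window.** Protocol 3.1 documents AEs, product complaints and device deficiencies "from the time of signing the informed consent form (ICF) through the End-of-Study/ Early Termination Visit". Protocol 5.5 requires a new consent and a new patient ID at re-enrolment.
- **Who can re-enrol.** Under Protocol 3.5.1, patients withdrawn over missed therapy caused by water device replacement "may be allowed to rescreen to re-enroll up to 1 time, as assessed by Investigator and Sponsor". SAP 7.3 states the permission more generally.
- **Device rates.** SAP 14.3.2 takes the event count, "dividing it by the total number of days the device is installed" in patients' homes. The formula beneath runs from home installation to last treatment.

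**The concern.** A rate per patient-year needs a denominator made of time in which an event would have been recorded. A re-enrolled patient has two observed periods separated by an off-study interval. The SAP gives one time origin (the first-ever treatment), one subject identifier and one span, with no term that removes the interval. It also does not say which completion or withdrawal date, or which of two consent dates, applies to such a patient.

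The study has one arm and no comparator, so a reader will judge an AE rate per patient-year as it stands. Re-enrolment is tied in the protocol to water device replacement, so any distortion comes from patients who had trouble with the device. The SAP applies per-enrolment logic elsewhere: section 16.1 matches each enrolment to its own baseline, and sections 13.1 and 14.1.1 restart the weeks in use for a new water device. The exposure formulas lack it.

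**Working it through.** The documents state no exposure total or AE rate, so there is no figure to reproduce. The check compares the SAP denominator with observed time.

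**From the documents:** 12 weeks of treatment = 84 days; follow-up 5 to 10 days (7 used); screening about 3 weeks plus baseline about 2 weeks = 35 days; target of 30 evaluable patients.

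**Assumed, not in the documents:** k re-enrolled patients; first enrolment stopped after 28 treated days; G days from first withdrawal to re-consent.

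**Treatment-emergent time, in days, with +1 per span**

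- One enrolment: 84 + 7 + 1 = 92.
- Re-enrolled, observed: first enrolment 28 + 7 + 1 = 36; second, from re-consent, 35 + 84 + 7 + 1 = 127; total 163. The second screening and training count as observed because consent has been signed and, under SAP 14.2.1 and 14.2.2, an AE then falls after the first-ever treatment and is treatment-emergent.
- Observed total: 92(30 − k) + 163k.
- Reading A, first-ever treatment to final exit: 92(30 − k) + k(162 + G).
- Reading B, first-ever treatment to first withdrawal: 92(30 − k) + 36k.
- Reading C, each enrolment ID measured from the first-ever treatment: reading A + 36k.

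The ratio is the SAP rate over the correct rate, i.e. observed time over SAP time.

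| k, G | Observed | A (ratio) | B (ratio) | C (ratio) |
|---|---|---|---|---|
| 1, 28 | 2831 | 2858 (0.991) | 2704 (1.047) | 2894 (0.978) |
| 3, 56 | 2973 | 3138 (0.947) | 2592 (1.147) | 3246 (0.916) |
| 5, 84 | 3115 | 3530 (0.882) | 2480 (1.256) | 3710 (0.840) |

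Reading A understates the rate by 0.9%, 5.3% and 11.8%. Reading B overstates it by 4.7% to 25.6%, because the second enrolment's events stay in the numerator while its time is dropped. Reading C counts the first enrolment twice. With k = 0, all readings give the observed time. With 50 patients and k = 5, G = 84, reading A gives 4955/5370 = 0.923.

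**All-AE time, from consent.** One enrolment is 35 + 84 + 7 + 1 = 127. Re-enrolled, observed, is (35 + 28 + 7 + 1) + 127 = 198. First consent to final exit is 197 + G. The ratios are 3881/3908 = 0.993, 4023/4188 = 0.961 and 4165/4580 = 0.909.

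**Placement of +1.** If it is added once instead of once per patient, 29 of 30 × 92 = 2760 days are lost: 29/2760 = 1.05%. This raises the rate.

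**Device-days for one re-enrolled patient.** Assume installation 35 days before first treatment in each enrolment. Installed intervals to last treatment are (35 + 28) + (35 + 84) = 182 days. First installation to final last treatment is 35 + 28 + 7 + G + 35 + 84 = 189 + G, or 245 days for G = 56. For that patient the ratio is 182/245 = 0.743.

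**The case against.** **The direction is not fixed.** A reader might infer that the AE rate is certainly understated. The documents do not support that: the SAP leaves the exit date undefined, and reading B overstates the rate. This stands as a limit on direction. It does not rescue the formula, since none of the three readings returns observed time once a patient re-enrols.

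**Few patients, supplementary statistic.** Re-enrolment is limited to one time and assessed by the investigator and the sponsor. Every k and G here is assumed. Protocol 10.6 asks for frequencies and percentages, and the table contents in SAP 14.2.4 name patients, percentages and events, none of which depends on patient-years. This is fair and limits the importance. Still, SAP 14.2.1 makes the rate a default part of AE summaries, and several SAP sections carry rules for re-enrolment, so the case is expected.

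**The gap is not wholly dark.** Protocol 6.8 follows serious AEs and adverse device effects after the study, and Protocol 7.2.3 requires late reporting of serious AEs that occurred during participation. Neither is routine collection of new AEs off study.

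**Alarms.** A reader might also infer that the alarm rate is understated, because installation days include days without treatment. With 14 to 35 installed days before treatment and a break of 0 to 14 days, 84 treatment days are 84/98 = 86% down to 84/133 = 63% of the denominator. That is not an error. SAP 14.3.2 openly labels the rate as per installation day. Device deficiencies are collected from consent, the water device stays on when not in use (Protocol 6.6), a simulated treatment precedes the first real one, and Protocol 8.10 foresees withdrawal over alarms before eligibility is confirmed. Alarms per treatment would be a different rate, not a correction.

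**Conclusion.** The point holds for the AE rates. For any re-enrolled patient, the SAP 14.2.1 rules (first-ever treatment date, one subject identifier, all events counted) do not produce observed patient-time. Under the natural reading the treatment-emergent rate is understated by about 1% to 12%, assuming 30 patients, 1 to 5 re-enrolled, gaps of 28 to 84 days and a first enrolment treated for 28 days. The all-AE rate is understated by about 1% to 9% on the same assumptions if the first consent date is used. The effect is nil if nobody re-enrols. The +1 placement is worth about 1% in the opposite direction if it is read as added once.

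For SAP 14.3.2 only two clarifications hold. The device-day formula does not say how off-study gaps are treated. Its wording also refers to days installed while the formula stops at last treatment, although the last simulated treatment follows the last treatment (Appendix 1, footnote u) and product return is scheduled in follow-up. That truncation shortens the denominator.

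**What to change.** In SAP 14.2.1, define exposure as a sum over enrolments:

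- **All AEs:** that enrolment's exit date minus that enrolment's consent date, + 1.
- **Treatment-emergent AEs:** in the enrolment containing the first-ever treatment, exit date minus first-ever treatment date, + 1; in any later enrolment, exit date minus re-consent date, + 1.
- Put the + 1 inside the sum, once per enrolment.

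The later enrolment should not start at its own first treatment. That would drop 35 observed days per re-enrolled patient whose AEs still count as treatment-emergent. The denominator would be 2760 + 36k, and the rate would be overstated by 1.3% (2831/2796, k = 1), 3.7% (2973/2868, k = 3) or 6.0% (3115/2940, k = 5).

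In SAP 14.3.2, sum device-days over each installed interval so that off-study gaps are excluded, and make the wording and the formula end on the same date. Alarms per treatment may be added as an optional extra; SAP 11.1 already reports diary items as "the total number of events per total treatments".

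The cost is SAP text and derivation code, with no new data collection. Compared with the natural reading, the reported AE rate becomes slightly less favourable.

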14.2.2 Classification of Adverse Events

Pre-treatment adverse event – An adverse event that starts between the date of signing the informed consent form (ICF) and the start of the first treatment.

Treatment-emergent adverse event (TEAE) – An adverse event that starts on or after the start of the first treatment.

In case of incomplete information on study treatment or AE onset, events will be classified as treatment-emergent unless there is sufficient data to rule out the possibility that the event started after the start of study treatment application.

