**Table 6. Definition of Terms**

Term	Definition
Awareness Date or Baxter Awareness Date (BAD)	The date on which any Baxter employee or their agent becomes aware of an adverse event (AE). This date is considered Day 0 on the regulatory reporting time clock.
Date of Onset	The date when the signs and symptoms of the AE begin.
Investigational Product (IP)	Experimental product under study or development. This term is more specific than investigational medicinal product, which includes comparators and placebos. For this protocol, the term “investigational drug” is synonymous with “investigational product”. For this protocol, the term “investigational product” is synonymous with AMIA APD Solution Generation System.
Diagnosis vs Complications	A patient experiences not only a diagnosis, but also additionally a complication of the diagnosis (i.e., myocardial infarction with congestive heart failure); both the diagnosis and the medical complication should be collected and recorded as separate AEs.

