## 7.2 Safety Reporting

All AEs, PCs and DDs observed by the study personnel or reported by the patient during the course of the study will be documented from the time of signing the ICF through the End-of-Study/ Early Termination Visit.

Any medical condition, that is present at the time that the participant is screened, will be considered medical history and not reported as an AE (see [Appendix 6](#)). Any medical event that is commonly associated with a study participant’s PD therapy will be considered medical history and not reported as an AE (see [Appendix 6](#)). However, if the study patient’s condition/event worsens (change in severity or frequency) at any time during the study, it will be recorded as an AE.

If a definitive diagnosis has been medically established by the physician caring for the patient or by the Investigator, this diagnosis should then be recorded as the AE on the eCRF and the signs and symptoms removed. If a definitive diagnosis has not been medically established, the signs and symptoms should then be recorded as the AEs.

Adverse events that change in severity will be reported at each incidence, but documented only once in the eCRF with the highest degree of severity.

An elective procedure/ surgery that occurs during the course of a study, but is being performed for a documented pre-existing condition and was pre-planned prior to study entry will not qualify as an AE. If, however, the pre-existing condition unexpectedly deteriorates during the study requiring the procedure/ surgery to be performed earlier than planned, the condition for which the procedure/ surgery is being performed will qualify as an AE.

Laboratory and vital sign abnormalities qualify as AEs if medical intervention is required to treat or address the abnormality, if the patient must be discontinued from the study due to the abnormality, or if the Investigator determines the value is clinically significant.

An AE can result from the use of the study product in accordance with the protocol, as well as from an accidental or intentional misuse of the study product or any other treatment error such as unintentional administration or use of another product during the course of the study.

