### **7.2.3 Adverse Events Reporting**

The PI shall:

- Record every AE with a full description.
- Follow-up or new information about an SAE should be provided by the Investigator or a designee using the SAE form within 24 hours of becoming aware of the new information.
- All non-serious AEs that are upgraded to an SAE should be forwarded to Baxter or designee within 24 hours.
- Supply Baxter or designee, upon Baxter's or designee's request, with any additional information related to the safety reporting of a particular event.
- Report any SAE if becoming aware after study completion has occurred in a patient during their participation in the study, the SAE must be reported on the SAE Form within 24 hours of awareness.
- If an event is part of the patient's medical history, it will not be considered as an AE for the study unless the frequency increases or the severity worsens.

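### Treatment-emergent status rests on start date alone, so an AE that begins before first treatment and worsens on the system is left out of every planned AE summary table

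*SAP*

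**What the plan says.** **Classification.** SAP 14.2.2 has two classes. A pre-treatment event is "An adverse event that starts between the date of signing the informed consent form (ICF) and the start of the first treatment". A TEAE is "An adverse event that starts on or after the start of the first treatment". There is one fallback: "In case of incomplete information on study treatment or AE onset, events will be classified as treatment-emergent", unless the data rule out a start after treatment began. SAP 16.2.3 adds rules for missing start dates only.

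**Onset and recording.** Protocol Table 6 defines date of onset as "The date when the signs and symptoms of the AE begin". Protocol 7.2 says that an AE whose severity changes is reported on each occurrence but "documented only once in the eCRF with the highest degree of severity". Protocol 7.2.3 treats a change in seriousness as an upgrade of the existing event: "All non-serious AEs that are upgraded to an SAE should be forwarded to Baxter or designee within 24 hours". For conditions held as medical history, protocol 7.2 differs: if the condition "worsens (change in severity or frequency) at any time during the study, it will be recorded as an AE".

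**Outputs.** All nine overview categories and all bulleted tables in SAP 14.2.4 are restricted to TEAEs. The table list in SAP section 17 adds no table of pre-treatment AEs or of all AEs. On listings, SAP 14.2.1 says: "If an adverse event changes in severity, then each severity will be listed".

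**The concern.** The AE and SAE profile on the system is a secondary endpoint of a single-arm study, so no control group offsets an undercount. Deterioration after a patient starts on the system is what the TEAE tables should show. A rule based on start date alone leaves that deterioration out when the first symptom came before first treatment.

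The rule also fits badly with the rest of the plan. A medical-history condition that worsens becomes an AE and can be counted, while an AE that arose after consent and worsens in the same way cannot. The SAP is conservative elsewhere: an unknown onset defaults to treatment-emergent, and a missing severity is set to severe (SAP 14.2.1). A known deterioration on treatment is thus handled less conservatively than a missing date.

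**Working it through.** The plan states no figure on this point, so the main check is to follow different event courses through the rules.

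| Course of event | How it is recorded | Class | In AE tables? |
|---|---|---|---|
| Starts in Screening or training, still open at first treatment, does not worsen | One record, early onset | Pre-treatment | No, and rightly so |
| Starts in Screening or training, then worsens or becomes serious on treatment under the same diagnosis | One eCRF record at highest severity (protocol 7.2), or an upgrade (7.2.3); onset at first symptoms (Table 6) | Pre-treatment | No: this is the gap |
| Medical-history condition worsens on treatment | Recorded as an AE (protocol 7.2, 7.2.2) | Treatment-emergent, if onset is dated at the worsening | Yes |
| New complication arises on treatment | Separate AE (Table 6) | Treatment-emergent | Yes |
| Onset unknown, and a start after treatment began not ruled out | One record | Treatment-emergent (SAP 14.2.2, 16.2.3) | Yes |
| Re-enrolled patient, AE starts in a later screening after an earlier treatment | One record | Treatment-emergent, because the first-ever treatment date is used (SAP 14.2.1) | Yes |

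Only the second row is affected. The fallback does not reach it, because onset and treatment date are both known.

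**Where a second-row event appears (SAP 14.2.4 and section 17).**
- Missing: all AE summary tables, and the treatment-emergent listings for device-related events, special-interest events and withdrawal.
- Present: the pre-treatment listing; if serious, the serious pre-treatment listing; if the patient died, the listing of AEs for patients who died. Withdrawals also appear with their primary reason in disposition (SAP 7.1, 7.3).

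**Exposure window.** Protocol 3.4 gives about 3 weeks of Screening, about 2 of Baseline, 12 of treatment and 5 to 10 days of follow-up.
- Before treatment: 3 + 2 = 5 weeks.
- Total: 3 + 2 + 12 + 5/7 = 17.7 weeks, to 3 + 2 + 12 + 10/7 = 18.4 weeks, in line with the stated 18 or so.
- Share before treatment: 5/18.4 = 27% to 5/17.7 = 28%. This is a share of calendar time, not of AEs.

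**Effect of one patient.** The Safety Set size is not stated. I assume 30 (the completer target) to 50 (the enrolment cap).
- 1/30 = 3.3 points; 1/50 = 2.0 points, in any row where the patient has no other qualifying event.
- One patient can decide entry to the table of TEAEs in at least 5% of patients: 1/30 = 3.3% against 2/30 = 6.7%, or 2/50 = 4.0% against 3/50 = 6.0%.

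**The case against.** The strongest reply is that the gap is narrow and the event stays in the report. Both parts stand. Medical-history worsening, new complications and later enrolments are already covered, as the table shows. The investigator must also find the patient clinically stable before home treatment (protocol 6.9, 8.4), which makes an evolving AE at first treatment less likely. AE listings show start and end dates, treatment start date, seriousness, outcome and device relationship, so a reader can see that an event ran past first treatment.

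Four stronger readings are tempting, and the documents do not support them.
- A reader might infer that every AE open at first treatment is misclassified. It is not: one that neither worsens nor becomes serious is pre-treatment under any sensible definition.
- A reader might infer that the event survives only in the pre-treatment listing. The serious pre-treatment, deaths and disposition outputs also carry it, and the SAP 14.3.2 summaries of device deficiencies resulting in an AE are not limited to TEAEs.
- A reader might infer that the database cannot hold a severity history. Protocol 7.2 asks for a report on each occurrence as well as a single eCRF entry, and SAP 14.2.1 promises each severity. The eCRF is not in the documents, so this is an ambiguity to resolve, not a proven data gap.
- A reader might take the 27 to 28% as the share of AEs affected. No event rate is given.

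It can also be argued that the tables are not purely treatment-emergent. Protocol 10.6 summarises AEs without that limit, SAP section 12 declares no change from the protocol, and SAP 14.2.1 defines patient-years for all AEs, including those before treatment. But no table in SAP 14.2.4 or section 17 is clearly assigned to that wider set, so this text does not bring the event back into a table.

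**Conclusion.** The point holds for a defined set: AEs that start after consent and before first treatment, are open at first treatment, and then worsen in severity or become serious under the same diagnosis. The rule as written keeps them out of every AE summary table and out of the treatment-emergent device-related, special-interest and withdrawal listings. The error runs one way, toward lower TEAE counts.

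The number of such events is unknown and may be small. The per-patient effect of 3.3 to 2.0 points depends on the assumed Safety Set of 30 to 50. The conclusion also assumes that worsening creates no new record with its own start date, and neither document says that it does. The primary endpoints are unaffected. The amendment is worthwhile because it corrects a stated rule for a secondary safety endpoint at little cost.

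**What to change.** 1. **SAP 14.2.2.** Define a TEAE as an AE that starts on or after first treatment, or that starts earlier and worsens in severity or becomes serious on or after first treatment.
2. **Reconcile protocol 7.2 with SAP 14.2.1**, so that the date of each severity change is available for both the classification and the promised listing. If severity changes are already captured, an eCRF completion instruction is enough. If they are not, make a short change to protocol 7.2 that requires a new record or a dated severity change when a pre-treatment AE worsens after first treatment.

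**Cost.** One sentence in the SAP, and slightly higher TEAE counts. If protocol 7.2 is changed, an amendment with IRB approval before implementation (protocol 11.2), an eCRF update and possibly queries on AE records already entered.
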